### 8.3 Safety Population

The Safety population includes all enrolled subjects who started the inhalation of study medication, whether the subject was in AF or not and whether the subject received the full assigned dose of study medication or not. Compared to the ITT population, the Safety population excludes subjects who are enrolled but did not start the inhalation of study medication.

Population includes Part A, Part B and Part C MLS subjects receiving 120 mg FleclH-103.

### 8.4 PK Population

The PK population includes all enrolled subjects who received the full assigned dose of study drug irrespective of whether the subject was in AF or not at the initiation of dosing. Compared to the Safety population the PK population excludes subjects who did not receive the full assigned dose of study drug. The full 120 mg dose of study medication is defined as completing both inhalation stages, for a total dose of 120 mg eTLD (2 x 60 mg eTLD).

Population includes Part A, Part B and Part C MLS subjects receiving 120 mg FleclH-103.

**FLE-002 (INSTANT) – Final Analysis****Statistical Analysis Plan**

Subject is in PK population, thus receiving the “full 120 mg dose of study medication”, if both conditions below apply:

**Condition 1: Medication was administered for a sufficient period of time**

According to protocol medication should be administered for at least 3.5 minutes in two inhalation stages, separated by a 1-minute break. To measure if subject completed study medication according to protocol the following information, as registered in the EDC, is used:

- Was first dose taken?  
SAS Dataset: EX, record for first dose, column: EXYN=1 (Yes) or 0 (No)
- If not: Reason first dose was not taken  
SAS dataset: EX, record for first dose, column: EXREASNS
- Was repeat dose started?  
SAS Dataset: EX, record for repeat dose, column: EXYN=1 (Yes) or 0 (No)
- If not: Reason repeat dose was not taken  
SAS dataset: EX, record for repeat dose, column: EXREASNS
- Start Time of First Dose  
SAS Dataset EX, record for first dose, column: EXSTTM (measured in seconds)
- End Time of First Dose  
SAS Dataset EX, record for first dose, column: EXENTM (measured in seconds)
- Start Time of Repeat Dose  
SAS Dataset EX, record for repeat dose, column: EXSTTM (measured in seconds)
- End Time of Repeat Dose  
SAS Dataset EX, record for first dose, column: EXENTM (measured in seconds)
- (Start) Time of Conversion to SR  
SAS dataset DSConv, record for first or second dose, column: DSSTIM (measured in seconds) indicates the time of conversion. This is the start of the 60 second period of SR that is required for index conversion.  
These conditions must apply for subject to meet Condition 1:
  - Was first dose taken: Yes
  - Was repeat dose taken: Yes
  - Total time of the administration of the First Dose and Second Dose is at least 6 minutes and 30 seconds (390 seconds), total administration time is measured as the sum of:
    - The difference between End Time of First Dose and Start Time of First Dose
    - The difference between End Time of Second Dose and Start Time of Second Dose.

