5.3.4 B – Administration

Subjects will be dosed with 120 mg eTLD (2 x 60 mg) FlecIH-103 (75 mg/mL) inhalation solution: 2 inhalations of 3.5 minutes each, separated by a 1-minute break ('dose/inhale to conversion'). Dosing in a 'dose/inhale to conversion' regimen continues until the conversion of AF to SR is observed for \geq 1 minute, or until the full dose is completed, whichever comes first.

For the administration of study drug, the following procedures are to be performed:

Study no. FLE-002

Version 8.0 EU-1 Page: 49 of 117

1. The subject must be seated in an upright position in a chair or adjustable bed from approximately 30 minutes prior to the start of inhalation up to completion of dosing, at which point subjects may return to a semi-recumbent position. A height-adjustable table must be placed in front of the subject (e.g., overbed table on casters), whereby the subject can rest his/her arms during the inhalation regimen. The set up at the site will allow for subject to remain in this upright sitting position while connected to the cardiac monitoring system and while blood samples are collected during the self-administration of the inhalation solution.

NOTE: Subjects may be placed in a semi-recumbent, supine, or other position as needed for an adverse event, at the discretion of the investigator. These occurrences will not constitute a protocol deviation.

- 2. The subject is given instructions from study personnel on how to inhale the study drug according to the IFU.
- 3. The subject is required to use a nose clip to seal off their nostrils during inhalation, unless the subject refuses.
- 4. The subject may practice the inhalation procedure (without flecainide) prior to starting the inhalation of study drug.
- 5. The inhaler must be connected to medical compressed air that is set at a steady flow rate of 5 L/min.
- 6. The subject shall be informed prior to the start of the inhalation about the potential to experience throat discomfort, bad taste, and the impact of the sensation caused by the vapors being inhaled.
- 7. If not contraindicated, a topical oral anesthetic (e.g., containing lidocaine or phenol) spray (e.g., Medica, Chloraseptic) or lozenge (e.g., Trachitol, Cepacol) may be used by the subject to prophylactically mitigate the discomfort or pain associated with the inhalation and thereby improve the tolerability.
- 8. The subject inhales the study drug using a fully assembled AeroEclipse® II BAN provided by the study nurse.

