**15 Programming Specifications**

If required, a separate document will provide details necessary to replicate the various data derivations outlined in the SAP.

**FLE-002 (INSTANT) – Final Analysis****Statistical Analysis Plan****Annex A: FLE-002 Sponsor Review of Adverse Events of Special Interest****1. Background and Justification**

- 1.1 FLE-002 (INSTANT) is the first InCarda Phase 2 clinical study to assess the efficacy and safety of flecainide acetate inhalation solution (FlecIH-103), administered via oral inhalation in patients with recent onset, symptomatic atrial fibrillation (AF). The study is composed of 3 parts which was refined over time through successive protocol amendments (Parts A, B, and C). Part A examined different formulations of inhalation solutions and dosages, leading to the selection of the 120 mg estimated total lung dose (eTLD) of FlecIH-103 formulation administered as two 3.5-minute inhalations separated by a 1-minute break (8 minutes total administration time). This treatment regimen was further evaluated in Parts B and C of FLE-002 and was selected for evaluation in Phase 3.
- 1.2 One of the main objectives of the study, and the focus of the final analysis, is to assess the safety of 120 mg FlecIH-103 inhalation for acute cardioversion of AF. To address this objective, Adverse Events (AEs) were collected by the sites and entered in the Case Report Form (CRF), implemented in an Electronic Data Capture (EDC) system. The AEs were initially also entered in the CRO's Safety Database by the safety team as the MedDRA and WHODrug coding feature in the EDC system (Marvin) was not enabled (in Part A).
- 1.3 Several AEs of special interest (AESIs) were defined for FLE-002, which were progressively refined in subsequent protocol amendments. In February 2021, InCarda amended the FLE-002 protocol (v8.0 EU-1; 16 Feb 2021) with the final pre-defined AESI list and associated criteria, which included: 1) AEs related to the inhalation device; 2) Pregnancy, and; 3) AEs known to be related to other well characterized flecainide formulations (i.e., IV and oral). Criteria for these AESIs and serious AESIs are further defined in Section 5.
- 1.4 Because the definition of AESIs changed over time, and the process to collect them varied between the different parts of the study, InCarda will centrally review all AEs and provide a consistent assessment of AESIs per the criteria described in Section 4 below.

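### SAP 8.4 takes the repeat-dose end time from the first-dose record; coded as written, a subject dosed to schedule computes as 150 s and fails the 390 s test for the PK population

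*SAP*

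**What the plan says.** SAP 8.4 requires two conditions for the PK population. The section first describes a full dose in words: "The full 120 mg dose of study medication is defined as completing both inhalation stages, for a total dose of 120 mg eTLD". Condition 1 then makes this operational. It lists dataset, record and column for each item and states a rule that uses those items.

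- **Source list.** *Start Time of Repeat Dose* comes from the repeat-dose record: "SAS Dataset EX, record for repeat dose, column: EXSTTM (measured in seconds". The items for whether the repeat dose was started, and why not, also point to the repeat-dose record. *End Time of Repeat Dose* does not. Its source is "SAS Dataset EX, record for first dose, column: EXENTM (measured in seconds". The same line appears, correctly, under *End Time of First Dose*.
- **Rule.** Both doses must have been taken, and "Total time of the administration of the First Dose and Second Dose is at least 6 minutes and 30 seconds (390 seconds"). The total is the sum of two terms: "The difference between End Time of First Dose and Start Time of First Dose", and "The difference between End Time of Second Dose and Start Time of Second Dose".

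The planned regimen is "2 inhalations of 3.5 minutes each, separated by a 1-minute break" (Protocol 5.3.4 B). SAP Annex A, item 1.1, agrees: "two 3.5-minute inhalations separated by a 1-minute break (8 minutes total administration time").

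**The concern.** The source list is the only place in the available text that says where the second-dose end time comes from. It names dataset, record and column, so it works as a programming instruction. Followed literally, the second term of the sum becomes the end of the first dose minus the start of the second. That is the break between inhalations with a negative sign.

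At stake is who enters the PK population. SAP Table 1 and sections 9.2.2.10, 9.2.2.11 and 6.2.5.2 use that population for flecainide concentrations over time and for the additional analyses of QRS and change in QRS. A wrong flag would remove subjects who did receive the full dose.

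A programmer who silently corrects the line gets the right population but departs from the written plan on population membership. SAP section 10, which lists differences from the protocol, says nothing on the point.

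**Working it through.** **Inputs**

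- Threshold: 6 min 30 s = 6 × 60 + 30 = 390 s (SAP 8.4, Condition 1). The plan's own conversion is correct.
- Inhalation stages: 3.5 min = 210 s each, with a 60 s break (Protocol 5.3.4 B; SAP Annex A, item 1.1).
- Resulting timeline: S1 = 0, E1 = 210, S2 = 270, E2 = 480 s. The elapsed time is 480 / 60 = 8 min, which matches Annex A.

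**Rule as worded**

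Total = (E1 − S1) + (E2 − S2) = 210 + 210 = 420 s. This meets 390 s with 30 s to spare.

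**Rule with the source line as written (E2 read from the first-dose record, so E2 is replaced by E1)**

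Total = (E1 − S1) + (E1 − S2) = 210 + (210 − 270) = 210 − 60 = 150 s. This misses 390 s by 240 s. The computed second-stage duration is −60 s.

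**What the miscoded total measures**

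Algebraically it is the first inhalation minus the break. The second inhalation drops out.

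- With a 60 s break, the first inhalation would have to last at least 390 + 60 = 450 s (7.5 min) to pass. That is 450 − 210 = 240 s longer than planned.
- With the first inhalation at 180 to 300 s and the break at 0 to 120 s (ranges assumed for illustration), the largest total is 300 − 0 = 300 s. Every combination fails.
- Removing the negative sign does not rescue it: 210 + 60 = 270 s, still below 390 s.

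**After correction (E2 from the repeat-dose record)**

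| First stage (s) | Second stage (s) | Total (s) | Meets 390 s |
|---|---|---|---|
| 210 | 210 | 420 | yes |
| 195 | 195 | 390 | yes |
| 180 | 210 | 390 | yes |
| 194 | 195 | 389 | no |
| 210 | 179 | 389 | no |

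The corrected rule admits subjects dosed to schedule and tolerates a combined shortfall of 30 s, as 420 − 390 implies.

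**The case against.** The strongest reply is that this is a copy slip whose intent is obvious. The item's label says repeat dose, its neighbours use the repeat-dose record, and the rule refers to the second dose's own end and start. A programmer could easily read it correctly. If not, a second-stage duration of −60 s and a nearly empty population would be conspicuous. SAP section 9 requires validation under the CRO's procedures, and section 15 allows a separate derivation document if one is required.

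Much of this stands. A reader might infer that the PK population will in fact be empty, or that every fully dosed subject fails. The documents do not support either statement. Both depend on literal coding against the label and the rule, and the program is not shown. Nor is *every* strictly proven: Protocol 5.3.4 B lets the inhalation time be extended after an interruption of more than 30 s. A first stage about 4 minutes longer than planned would be needed to pass.

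A reader might also infer that the mITT population, and so the primary endpoint, is affected, because SAP 8.5 describes completing the dose in similar words. But 8.5 cites neither this field nor the 390 s threshold. An effect would require the programmer to reuse the Condition 1 flag, which nothing in the text directs.

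The reach within PK is limited too. The Cmax-threshold secondary endpoint uses the mITT population (SAP 9.2.2.1). The ECG parameters are also reported for the Safety population. Most summary PK statistics are calculated outside the final report (SAP 9.2.2.10).

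What the reply does not remove is that the written derivation names the wrong record and gives no other source for the second-dose end time.

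**Conclusion.** The derivation is wrong as written and should be corrected. Coded literally, a subject dosed to schedule gets 150 s instead of 420 s against a threshold of 390 s. Subjects dosed to schedule would then be wrongly excluded from the PK population and from the PK and additional QRS summaries based on it. No effect on the primary endpoint is shown.

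The size of the error assumes the planned timeline of two 210 s inhalations and a 60 s break. Whether it reaches the results depends on the program, which the documents do not show. The text of the second condition for the PK population was not available for this review, so the complete algorithm could not be checked. This is a small specification error with a clear remedy. It is not a flaw in the design.

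**What to change.** In SAP 8.4, Condition 1, change the source for *End Time of Repeat Dose* to dataset EX, record for repeat dose, column EXENTM. As an optional safeguard, add a check that each stage duration is positive before the 390 s test is applied. If the population flag has already been programmed, confirm which record the code reads.

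The cost is a one-word correction. It needs no new data, no change to the threshold and no change to the design.

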**FLE-002 (INSTANT) – Final Analysis****Statistical Analysis Plan****8.5 Modified Intention-To-Treat Population (mITT)**

The modified ITT population includes all enrolled subjects who completed the full assigned dose of study drug and were in AF at the time of start of the inhalation of the study drug. Subjects whose AF converted to SR prior to completion of the assigned full dose of study drug will also be included in the mITT population.

Completing the assigned dose of study medication in accordance with the protocol (i.e., dose/inhale to conversion) is defined as completing both inhalation stages, for a total dose of 120 mg eTLD (2 x 60 mg eTLD), OR completing the dosing early due to conversion of AF to SR. All subjects who converted prior to completion of the assigned 120 mg dose of study medication will be included in the mITT population, regardless if they stopped dosing or continued.

The mITT population will be used to evaluate all primary and secondary efficacy endpoints. Population includes Part A, Part B and Part C MLS subjects receiving 120 mg FlecIH-103.

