5.5 B – Discontinuation Criteria

Subjects who are enrolled but who do not receive study drug (e.g., due to spontaneous conversion of their AF to SR prior to dosing) are considered early terminations. The subjects may be replaced and can re-screen for the study.

At any time during the study and without giving reasons, a subject may decline completion of the assigned study treatment. Study treatment may also be discontinued at the discretion of the Investigator as deemed appropriate for safety and/or if the subject's medical condition contraindicates further study treatment.

Follow-up and data collection continue until EOS for all enrolled subjects who received study drug, unless the subject explicitly withdraws consent for further clinical follow-up and data collection. If a subject withdraws consent for further collection of study data, their data up to that point are evaluated, and the reason for the termination is recorded in the eCRF. If termination of treatment or of clinical follow-up is a result of an AE or death, the AE must be recorded in the eCRF, including any changes in concomitant medications.

INSTANT Study Clinical Study Protocol

Study no. FLE-002

Version 8.0 EU-1 Page: 53 of 117

For subjects who cannot be located for their follow-up contacts, every reasonable effort must be made to make contact. The subject is considered "lost to follow-up" when contact with the subject has been lost without completing Day 5, and every attempt to contact has failed. Final documentation regarding all attempts to contact the subject shall be documented in the subject source records. All premature terminations of either study treatment or of clinical follow-up are tabulated and reported.

A subject's decision to withdraw from the study and/or to disallow further clinical follow-up is acceptable for any reason, without prejudice or detriment to their medical care, and the subject will not suffer any disadvantage as a result.

An excessive rate of subjects who withdraw consent or subjects lost-to-follow-up could render the study difficult to interpret. Hence, unnecessary withdrawal of subjects shall be avoided. Should a subject withdraw or be withdrawn, every effort must be made to contact the subject for a final follow up.

The Sponsor has the right to terminate the study, any part of the study, or the HHE Sub-Study at any time. In this event, the investigator(s) and relevant authorities will be informed of the reason for study termination.

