10.1.3 B - Modified ITT population (mITT)

The modified ITT population includes all enrolled subjects who received the full assigned dose of study drug and were in AF at the time of start of the inhalation of the study drug. Subjects whose AF converted to SR prior to completion of the assigned full dose of study drug will also be included in the mITT population.

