10.2.1 B - Efficacy analyses

Modified ITT population

The mITT population will be used to evaluate all primary and secondary efficacy endpoints.

Statistical analyses of secondary efficacy endpoints

Hierarchical testing and adjustments for multiplicity will not be applied in the evaluation of efficacy.

INSTANT Study Clinical Study Protocol

Study no. FLE-002

Version 8.0 EU-1 Page: 73 of 117

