**Imputation of other missing values**

No imputation is planned for other missing values, nor is any sensitivity analysis planned. Missing values are assumed to be Missing Completely at Random (MCAR).

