## FLE-002 (INSTANT) – Final Analysis

## Statistical Analysis Plan

Table 1: Analysis Populations by Characteristics

Data Type	MLS Populations		
	Safety 	PK 	miITT 
Demographics 	1,2,3,4	1,2,3,4	1,2,3,4
Efficacy	-	-	1,2,3,4
Safety	1,2,3,4	-	-
PK		2,3	
PD	1,2,3,4	2,3	

The numbers in the table denote each Cohort as follows (each are further defined in section 8.7):  
 1-Part C MLS Cohort;  
 2-Pooled MLS Cohort;  
 3-Pooled MLS No Predose Flecainide Cohort;  
 4-Pooled MLS Predose Flecainide Cohort.

 Safety, PK and miITT populations are defined below in section 8 of the SAP

Including medical history, prior and concomitant medications, patient characteristics, etc.

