## FLE-002 (INSTANT) – Final Analysis

## Statistical Analysis Plan

Analysis is performed for the mITT population. A Subject meets the endpoint if conversion occurred within 90 minutes after initiation of dosing without the use alternative medication (e.g., IV flecainide and propafenone) or procedures (e.g., ECV). If a subject's conversion status is unknown, then the analysis will assume that the subject did not convert.

The percentage is calculated as:

$$p = 100 * (\text{number of converted subjects} / \text{number of subjects in mITT population})$$

A 90% exact binomial confidence interval will be calculated for the percentage.

No formal testing will take place. Analysis will not be performed for the PLS population.

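### The only efficacy population for the medically-led study drops subjects who start dosing in AF and stop early without converting, and no analysis of all subjects dosed in AF is planned beside it.

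*SAP*

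**What the plan says.** SAP 8.5 states: "The modified ITT population includes all enrolled subjects who completed the full assigned dose of study drug and were in AF at the time" inhalation started. Protocol 10.1.3 B has the same requirement and adds: "Subjects whose AF converted to SR prior to completion of the assigned full dose of study drug will also be included". SAP 8.5 then spells out that dosing counts as complete if both inhalation stages are finished, or if the subject finished early because AF converted. It also keeps everyone who converted before the end of the dose, whether or not they went on inhaling.

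Early stopping for other reasons is foreseen. Protocol 5.5 B: "At any time during the study and without giving reasons, a subject may decline completion of the assigned study treatment". Protocol 6.2.1 B lets the investigator end inhalation for clinically significant arrhythmia or a serious reaction such as hypotension.

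Protocol 10.2.1 B: "The mITT population will be used to evaluate all primary and secondary efficacy endpoints". In SAP Table 1 the efficacy row is filled for the mITT only; it is blank for the Safety and PK populations, and ITT is not a column. The denominator of the primary endpoint in SAP 9.2.1 is the mITT. On sensitivity analyses, the part of SAP 7.2.5 that deals with other missing values says: "No imputation is planned for other missing values, nor is any sensitivity analysis planned". None for the choice of population appears elsewhere.

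For a subject inside the mITT whose conversion status is unknown, SAP 9.2.1 says "then the analysis will assume that the subject did not convert". The same section says "No formal testing will take place".

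**The concern.** Keeping a subject who stops because AF has converted is right under a regimen of inhaling until conversion. The difficulty is the other half of the rule. Take two subjects who start in AF and both stop before the end of the dose. The one who converted is kept and counted as a success. The one still in AF leaves the denominator.

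The reasons for stopping without conversion may themselves be related to outcome. If these subjects convert less often than those kept, the conversion rate and both limits of its 90% interval are too high. If they convert more often, they are too low. SAP 9.3 pools Parts A, B and C, which narrows the interval but does nothing to this bias. The protocol synopsis replaces non-completers to hold the mITT sample size, so further recruitment does not bring them back into the estimate.

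The rule also fits poorly with SAP 9.2.1. Inside the mITT, a subject of unknown status is counted as a failure. A subject who stopped early and was observed to remain in AF is not counted at all.

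A smaller gap concerns a subject who stops early in AF and then converts within 90 minutes. One sentence of SAP 8.5 requires stopping because of conversion. Another admits all who converted before completing the dose, whether they stopped or continued. The text most naturally describes conversion during dosing (compare Protocol 5.3.4 B, item 11) and does not say where the late converter belongs.

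**Working it through.** **The plan's own figures.** The protocol synopsis gives 25 subjects, a null rate of 20%, rejection at 9 or more conversions, and power of at least 92% at 48%. Exact binomial calculation gives P(X ≥ 9) = 0.0468 at 20% and 0.920 at 48%. For 9/25 the 90% Clopper-Pearson interval is 20.24% to 54.39%. All agree with the protocol.

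**Inputs.** Protocol 1.4 gives 29 subjects treated with 120 mg FlecIH-103 in Part A, with 13/27 converted and 2 excluded for an incomplete dose. For FlecIH-102 at the same dose it gives 19 treated and 2 excluded; that formulation is not in the pooled analysis. The outcomes and starting rhythm of the excluded subjects are not given. These figures also predate the mITT revision listed under V4.1 in the SAP version history, so some of these subjects might be included under the current rule. What follows is an illustration.

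**Part A FlecIH-103, all 29 counted, assuming both excluded subjects were in AF (90% Clopper-Pearson).**

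| Conversions among the 2 excluded | Rate | 90% CI | mITT rate minus this rate |
|---|---|---|---|
| mITT, 2 left out | 13/27 = 48.1% | 31.3 to 65.3 | – |
| 0 | 13/29 = 44.8% | 28.9 to 61.6 | +3.3 points |
| 1 | 14/29 = 48.3% | 32.0 to 64.8 | −0.1 points |
| 2 | 15/29 = 51.7% | 35.2 to 68.0 | −3.6 points |

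**Bias in general.** Let s be the share of subjects dosed in AF who are excluded, p the rate in those kept, and q the 90-minute rate in those excluded. The rate in all subjects dosed in AF is (1 − s)p + sq, so the mITT rate exceeds it by s(p − q). With p = 13/27:

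| s | q = 0 | q = 20% | q = 48.1% |
|---|---|---|---|
| 2/29 = 6.9% | 3.3 | 1.9 | 0.0 points |
| 2/19 = 10.5% | 5.1 | 3.0 | 0.0 points |

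**Pooling.** The interval for 13/27 is 65.3 − 31.3 = 34.0 points wide. Assume 27 Part A and 25 Part B mITT subjects at the same rate, before any Part C subjects. Then 25/52 = 48.1% has an interval of 36.0 to 60.3, which is 24.2 points wide before rounding of the limits. The interval shrinks while s(p − q) does not.

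**Part B rule, for context only.** Let r be the true rate in all subjects dosed in AF. The rate in the mITT is (r − sq)/(1 − s). With s = 2/29 and r = 20%:

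| q | mITT rate | P(X ≥ 9 of 25) |
|---|---|---|
| 0% | 21.5% | 0.069 |
| 10% | 20.7% | 0.057 |
| 16% | 20.3% | 0.051 |
| 20% | 20.0% | 0.047 |

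At r = 16% and q = 0 the mITT rate is 17.2% and the probability is 0.019. A borderline result is sensitive to a single subject: 9/25 has a lower limit of 20.24%, while 9/26 has 19.4%.

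**The case against.** The strongest reply is that little depends on this. The final analysis is exploratory, and Part B has already been tested and pooled. In Part A FlecIH-103 the shift is at most 3.3 points up or 3.6 down, against an interval 34 points wide, with an unknown sign. No subject is known to be excluded under the current wording. The Part B error of 0.069 needs early stoppers never to convert; if they convert at the same 20% as everyone else, there is no inflation. All of this stands. It limits the severity and is why the Part B figures are context only.

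A second reply is disclosure. SAP 8 plans a consort diagram with counts by population and cohort, and SAP 14 puts all data for dosed subjects in listings. A reader could divide the mITT conversions by the Safety count. That gives only a floor, because the Safety population includes subjects not in AF and any excluded converters are missed. It is not a planned rate with an interval.

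Three narrower points are fair. The rule on unknown status governs subjects already in the population, so the mismatch with SAP 9.2.1 is one of principle, not a contradiction. The no-sensitivity-analysis statement belongs to the missing-values text. The patient-led part reports conversion in every treated subject, but only three were treated.

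Finally, the mITT is pre-specified, and SAP 11 allows further analyses in the study report. That permits the missing table but does not commit anyone to it.

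**Conclusion.** The concern holds. As written, entry to the MLS efficacy denominator depends on the outcome among subjects who stop early, and no planned table gives the conversion rate with the excluded subjects counted. At the exclusion share seen in Part A FlecIH-103 (2/29), the mITT rate could be up to 3.3 points too high or 3.6 too low. At the FlecIH-102 share (2/19), it could be up to 5.1 points too high. These sizes take 48.1% as the rate in those kept and assume that the excluded subjects were in AF and would still be excluded under the current rule. The documents confirm none of these assumptions for Parts B or C.

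No stated decision is overturned: all the FlecIH-103 lower limits remain above 20% and the final analysis makes no test. What is affected is the credibility of the main efficacy estimate and its interval. This should be fixed, because the remedy is small and uses data already collected.

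**What to change.** Keep the pre-specified mITT. In SAP 9.2.1 and Table 1, add an analysis of the primary endpoint in all subjects who started inhalation while in AF, for Cohorts 1 to 4, with the 90% exact interval. Count an early stopper as not converted unless the index conversion occurs within 90 minutes of the start of dosing without other therapy. Show it beside the mITT result, together with the number of subjects the mITT leaves out, their reasons for stopping and their 90-minute outcomes. Add one sentence to SAP 8.5 that says how a subject who stops early in AF and converts later is classified.

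The cost is one table and one sentence. No new data are needed: Protocol 7.1 B has Holter recording to 90 minutes post dose, and Protocol 5.5 B continues follow-up for every subject who received study drug unless consent is withdrawn. The only drawback is that a slightly lower conversion rate may appear beside the mITT figure.
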